**References:**

WHO: <http://www.who.int/en/>

At baseline (for example during CT-simulation), during weekly OTVs, and at their 1-month post-RT follow-up appointment, intraoral photo-documentation will be taken and uploaded into patient specific Cerner electronic medical record charts utilizing the Cerner Camera Capture application via handheld mobile devices. These will be filed with study identifier only and not the subject name.

Patient reported assessment of OM will be evaluated at baseline (for example during CT-simulation), at OTVs during weeks 2, 4, and 6 of RT, and at their 1-month post-RT follow-up appointment, with the OMWQ (6) and PRO-CTCAE. The OMWQ questionnaire contains 9 items with the total ranging from 0 to 54.

Whole Unstimulated Saliva (WUS) will be collected at baseline (prior to first treatment), at OTVs during weeks 2, 4, and 6 of RT, and at the 1-month post-RT follow-up appointment. Further information on WUS collection and analyses is provided in Appendix A.

Microbiome samples will also be collected at baseline (prior to first treatment), at OTVs during weeks 2, 4, and 6 of RT, and at the 1-month post-RT follow-up appointment, immediately following collection of patient WUS. Further information on microbiome collection and analyses is provided in Appendix B.

## **7.2 Pre-medications**

Not applicable

## **7.3 Rescue Medications**

Not applicable

## **7.4 Excluded medications/treatments**

Orally topical or systemic antibiotic agents (such as chlorhexidine, nystatin, poviodine-iodine, clotrimazole, clindamycin, benzoydamine, etc) are not allowed and are not to be used within 7 days prior to registration. Directed antibiotics prescribed during or after RT for suspected infection related to treatment (ie oral thrush, neck abscess, cellulitis, etc) are allowed but will be documented appropriately.

# **8.REQUIREMENTS FOR TREATMENT**

## **8.1 Standard dose/treatment/device use**

The standard dose of ClōSYS® Unflavored Oral Rinse for the prevention and treatment of plaque build-up and halitosis is 15 ml (containing 0.1% [w/v] stabilized chlorine dioxide) for 30 seconds twice daily, which equates to a total of 30 mg of chlorine dioxide exposure over the oral mucosa. This dosage is the FDA approved and manufacture recommended amount (19)(20). Two randomized trials for the treatment of halitosis also utilized a similar dosage and found no significant adverse effects when compared against a placebo rinse (4)(21).

## **8.2 Dose IP/intervention/device modification**

Dose modifications will be considered at weekly OTVs during patient evaluations, should the patient report bothersome effects thought to be associated with use of the rinse. Dose reduction will occur by eliminating the PM rinse for one week followed by further assessment at the following OTV (approximately 7 days later). Should the patient continue to describe bothersome effects thought likely due to the rinse, the patient will be taken off the rinse at the discretion of the treating physician following discussion with the patient.

## **8.3 IP treatment/intervention/devise delays**

Subjects will begin oral rinsing the morning of day 1 of RT. The IP will be used twice per day continuously to the evening prior to their 1-month post-RT follow-up visit. If RT interruptions occur while taking the IP, subjects should continue IP per protocol, and additional IP may need to be given to the patient to complete the

schedule of treatment. All subjects will take a full continuous course of IP unless instructed by the PI to discontinue because of unacceptable toxicity as deemed appropriate by the PI. Subjects will be advised to rinse with the IP (preferably following meals) at 8 am ± 3 hours and 8 pm ± 3 hours.

If a subject misses a scheduled dose of IP within the recommended window, they should skip the missed dose and resume treatment at the next scheduled time. Treatment course will not be extended beyond the 1-month post-RT follow-up to compensate for missed doses. Subjects will stop treatment on the evening prior to their 1-month post-RT follow-up appointment with their Radiation Oncologist and return any remaining unused IP as described in Section 5.

If more than 7 consecutive days are missed of rinsing with the IP, the patient will be taken off study.

#### **8.4 Definition of a Dose Limiting Toxicity (DLT)**

Subjects will continue on IP twice daily from day 1 of RT to the evening prior to their 1-month post-RT follow-up appointment with their Radiation Oncologist or unless instructed to stop IP as described elsewhere. If the subject meets the criteria listed above to be taken off the study, they will discontinue IP, but all assessments will continue to be collected. There are no known pre-specified DLTs associated with the IP.

### **9. STUDY PROCEDURES**

#### **9.1 Screening and Baseline**

Potential subjects will enter the screening period of the study after a completely executed informed consent has been obtained. See Section 26 (Study Schedule) for full list of baseline evaluations.

#### **9.2 Registration/Randomization**

All regulatory requirements must be in place prior to subject registrations.

Single center study subject identification be assigned sequentially. Screen failure and subjects who withdraw prior to registration will have –“SF” or “WD” added to the end of the subject ID.

The stratification/randomization procedure utilized will be created and will employ a system of prepared envelopes and blocks of random numbers.

#### **9.3 On IP treatment/Intervention/Device**

Registered subjects will be treated with either ClōSYS® Unflavored Oral Rinse (0.1% w/v) at 15 ml per rinse for 30 seconds each twice daily or placebo oral

rinse at 15 ml per rinse for 30 seconds each twice daily, from the morning of day 1 of RT to the evening prior to their 1-month post-RT follow-up appointment with their Radiation Oncologist. Subjects will be instructed to place the rinse in their mouth, continuously swish and gargle the solution, and spit the rinse out after 30 seconds, without swallowing the rinse. It will be requested that they do the rinse at 8am (+/- 3 hours) and 8pm (+/- 3 hours) each day that they are receiving radiation treatments. In addition, they will be requested to do the rinse twice per day on weekends even though they do not receive radiation treatment on the weekends. Once starting the IP subjects will be asked to complete a rinse diary with the time, date, and duration of each rinse taken. They will also be asked to complete a patient observation form listing any side effects and/or problems with using the rinse that they may encounter.

See Section 26 (Study Schedule) for weekly evaluations while on IP.

#### **9.4 End of IP treatment/Intervention/Device**

Subjects will complete IP the evening prior to their 1-month post-RT follow-up appointment with their Radiation Oncologist.

#### **9.5 Follow up**

Subjects will be seen for one month [+21 days] follow-up visit after the end of RT. During these visits, routine vitals, review of systems, physical examination, and adverse event documentation will be performed. See treatment plan calendar. Additionally, any remaining unused IP, rinse diary, and observation forms will be collected. Patients will complete their final OMWQ and PRO-CTCAE, have OM scored by their treating physician, and have their final WUS and microbiome samples collected.

See Section 26 (Study Schedule) for weekly evaluations while on IP.

#### **9.6 Early Treatment Termination**

Subjects that terminate IP treatment prior to completing the planned treatment portion of the protocol will still be seen as per the study schedule and have an early termination visit at their 1-month post-RT follow-up appointment with their Radiation Oncologist. However, if the subject decides to withdraw from the study, no further information will be collected.

#### **9.7 Off Study**

Subjects will be considered off study after their 1-month post-RT follow-up appointment with their Radiation Oncologist.

### **10.PHARMACOKINETIC STUDIES**

Not applicable.

## 11. DATA AND SAFETY MONITORING PLAN

### 11.1. Identification of the DSMB obligated for oversight responsibilities:

The University of Arizona Cancer Center Data (UACC) and Data Safety Monitoring Board (DSMB) will provide ongoing oversight for this trial. UACC will act as the DSMB of record. The Clinical Trials Office (CTO) QA/QC team, the UACC DSMB's monitoring arm, will ensure operational integrity to study operations through regular monitoring visits. This study has been assigned institutionally as a Low Risk level by the UACC DSMB.

### 11.2. Identification of the entity obligated for routine monitoring duties:

Routine monitoring will be provided by the University of Arizona Cancer Center Quality Assurance/Quality Control (QA/QC) Program to ensure that the investigation is conducted according to protocol design and regulatory requirements.

The investigator will perform real time monitoring by reviewing UACC QA/QC periodic reports within 2 weeks of receipt. The PI and the study team will review data monthly to ensure patient safety and integrity of data.

All visits will be conducted according to the FDA principles described in the Code of Federal Regulations and following pertinent Guidance.

### 11.3. Monitoring progress and data review process:

Routine monitoring of subject data will be conducted at least quarterly by the UACC QA/QC Program.

The first routine monitoring visit will include at a minimum:

- Informed consent – 50% of cases enrolled;
- Subject eligibility – 10% of cases, up to two subjects;
- Data review – 10% of cases, up to two subjects.

All subsequent monitoring visits will consist of randomly selected subject cases based on current enrollment and include continuing review of previously selected cases, as applicable.

A monitoring visit report and follow-up letter will be completed approximately two weeks after the routine monitoring visit; a copy will be maintained in the study file. The monitor will request additional source documentation, clarification, information, or corrections to the CRF and/or regulatory records from the Clinical Research Coordinator (CRC) or other applicable staff responsible for the study and resolution of queries/findings. Documentation of such a request will be maintained with a copy of the monitor's visit report for follow-up at the next monitoring visit. Electronic records will be available in the institutional database or provided by the QA/QC Program staff.

The Principal Investigator will ensure the accuracy, completeness, legibility, and timeliness of the data reported in the Case Report Form (CRF), or other acceptable data formats. Source documentation supporting the study data should indicate the subject's participation in the trial and should document the dates and details of study procedures, adverse events, and patient status.

Case report forms, including but not limited to the inclusion/exclusion criteria form, adverse event and serious adverse event forms, and rinse compliance forms will be completed via the institution database, Redcap. Trials using paper CRFs will have the data entered with a black ball-point pen or typed. Corrections to the forms should not obscure the original entry and should be made by striking the incorrect information with a single line. Each strike should be accompanied by the initials of the corrector and the correction date. All subject forms and study files will be stored in a secure area limited to authorized staff.

**Note:** Routine monitoring of regulatory documents will be conducted at least annually by the UACC QA/QC Program.

The Radiation Oncology Staff will generate Case Report Forms (CRFs) for this study. Entries made in the CRF must be either verifiable against source documents, or have been directly entered into the CRF, in which case the entry in the CRF will be considered as the source data. The source data parameter to be verified and the identification of the source document must be documented. Corrections to CRFs and source data will be made only by authorized members of the study staff, clearly entered, initialed, and dated. The Investigator will sign a final CRF to indicate that, to his/her knowledge, they are complete and accurate. If further changes are made after this, the Investigator will be made aware of the corrections and his/her approval will be documented by re-signing.

As well, the study may be audited by regulatory agencies at any time. applicable regulatory agencies, and/or applicable ethical review boards with direct access to the original source documents.

The following topics are planned to be reviewed during each visit. Additional subject matter as appropriate will also be reviewed.

Initiation Visit: The initiation visit will be conducted soon after initiation of the Study.

1. Protocol
2. Credentials of key personnel
3. Facility readiness
4. Study products storage
5. Approval by the appropriate IRB
6. All study forms, including the informed-consent form and case report forms
7. Eligibility criteria
8. Randomization of subjects

Mid-study Visit: The mid-study visit will be scheduled after enrollment of about 60% of the total number of subjects.

1. Any change in key personnel
2. Workflow of the study

3. Informed consent form for subjects enrolled after the initiation visit
4. Eligibility criteria for subjects enrolled after the initiation visit
5. Protocol violations and deviations, if any
6. Any changes in the facility
7. Budget and payments
8. Subject dropouts
9. Adverse events reporting, if any

Closeout Visit: The closeout visit will be conducted after completion the Study.

1. Any change in key personnel
2. Informed consent form for subjects enrolled after the mid-study visit
3. Eligibility criteria for subjects enrolled after the mid-study visit
4. Protocol violations and deviations, if any
5. Any changes in the facility
6. Subject dropouts
7. Case report forms for all subjects
8. Corrections of data by authorized personnel
9. Adverse events reporting, if any
10. Completeness of all site source documents
11. Final accountability of all IP

#### **11.4 Process to implement study closure when significant risks or benefits are identified:**

If a Common Terminology Criteria for Adverse Events (CTCAE Version 5.0) grade 5 toxicity occurs that is more likely than not, directly related to the IP or placebo rinse, the study will be discontinued.

#### **11.5 Description of adverse events and reporting procedures:**

##### **ADVERSE EVENTS**

An adverse event (AE) is any untoward medical occurrence in a patient or clinical investigation subject administered a pharmaceutical product and that does not necessarily have a causal relationship with this treatment. An AE can therefore be any unfavorable and unintended sign, symptom, or disease temporally associated with the use of a medicinal (investigational) product, whether or not related to the medicinal (investigational) product.

Adverse events will be recorded on the UACC adverse events record form and reviewed by the Principal Investigator. For this study we will focus on collecting the AEs that may be related to the investigational product and/or radiation therapy/chemotherapy with specific focus on generalized weakness, skin reaction, weight loss, dry mouth, sore throat, dysphagia, anorexia, dysgeusia, voice alteration, and neck edema.

All adverse events will be classified using NCI Common Terminology Criteria for Adverse Events (CTCAE) version 5.0 and will address:

- Grade

- Relationship to study drug (not related, unlikely, possible, probable, definitely)
- Relationship to radiation and/or chemotherapy (not related, unlikely, possible, probable, definitely)
- Causality other than study drug (disease related, concomitant medication related, intercurrent illness, other)
- Date of onset, date of resolution
- Frequency of event (single, intermittent, continuous)
- Event outcome (resolved, ongoing, death)
- Action taken (none, held, dose reduced, discontinued, medication given)

## SERIOUS ADVERSE EVENTS

A serious adverse event (SAE) is any untoward medical occurrence that at any dose:

- 1) Results in death;
- 2) Is life-threatening;
- 3) Requires in-patient hospitalization or prolongation of an existing hospital stay;
- 4) Results in disability persistent or significant disability/incapacity, or;
- 5) Is a congenital anomaly/birth defect.

**Note:** A SAE may also be an important medical event, in the view of the investigator that requires medical or surgical intervention to prevent one of the outcomes listed above.

All serious adverse events, regardless of attribution, and any deaths will be reported within 24 hours of notification of the event to the sponsor and, if applicable, any collaborating entity. All serious adverse events and any deaths will be reported to the DSMB and to the University of Arizona Human Subjects Protection Program per the guidelines set forth in University of Arizona Cancer Center Data and Safety Monitoring Board Charter, Table 5: Adverse Event Reporting.

All submitted serious adverse events will be processed by the DSMB Coordinator monthly for initial trend analysis and then reviewed by the DSMB Chair. The assigned QA/QC Monitor will review the SAE reporting process to confirm reporting requirements are met.

### **11.6 Plan for assuring data accuracy and protocol compliance:**

Routine study activity and safety information will be reported to the DSMB on a quarterly basis, or more frequently if requested. These reports will include:

- Study activity, cumulative and for the period under review;
- Safety (narrative description on non-serious and serious adverse events);
- Predetermined protocol early stopping rules for efficacy/futility;
- Monitoring and protocol compliance;
- Comments;
- Attachments (AE data reviewed by the PI to compile the report, SAE letters and reports, results of any review(s), applicable correspondence with the IRB or other regulatory agencies.

Data, safety and study progress will be reported to:

- Human Subjects Protection Program (IRB) at least annually;
- Sponsor (if applicable) at least every six months.

#### **11.7 Identification of the sponsor or funding agency, as applicable:**

The PI will immediately notify, in writing, the funding agency, if applicable, any action resulting in a temporary or permanent suspension of the study. A copy of this correspondence will also be forwarded to the DSMB and the Scientific Review Committee (SRC).

### **12. ADDITIONAL SAFETY REPORTING REQUIREMENTS**

Serious adverse events will be reported to the Data Safety Monitoring Board as well as the institutional IRB within 24 hours of notification of the event to the PI. Serious adverse events will be reported using the FDA MedWatch form to inform the DSMB, and Report information that is Potentially Problematic to the institutional IRB.

### **13. QUALITY ASSURANCE MEASURES**

Per the UACC DSMB Charter, Internal *Ad Hoc* audits may be performed on any UACC clinical trial if identified for audit, the audit will be conducted by an identified audit team per the UACC DSMB Charter. A QA/QC representative will coordinate the audit team functions and a written audit report will be provided to the principal investigator and the DSMB.

### **14. RECIST CRITERIA**

Not applicable

### **15. REMOVAL OF SUBJECTS**

Subjects have the right to withdraw from the study at any time and for any reason without prejudice to their future medical care by the physician or at the institution. If this occurs, the investigator, or designee, is to discuss with the subject the safe and appropriate processes for discontinuation from the investigational product, intervention or device.

Subjects that wish to discontinue active IP treatment/intervention/device may elect to continue with the other protocol required assessments. The investigator should discuss with the subject the options for continuation of the study schedule of assessments (i.e. blood work, scans, physical exams, diaries) and collection of data, including endpoints and adverse events.

The investigator or designee must document the change in status of the subject's participation in the study and as applicable, the level of follow up that is agreed to

by the subject (i.e. agrees to follow up exams, adverse event review, phone contact, but not to further treatment and/or procedures).

Subject withdrawal of consent for a study indicates that the subject does not wish to receive further protocol required therapies or procedures, and the subject does not wish to, or is unable to continue further study participation. Subject data only up to the time when consent is withdrawn will be included in the analysis of the study.

## **16. STATISTICAL CONSIDERATIONS**

The primary statistical analysis will compare the proportion of patients who develop severe OM ( $\geq$ WHO Grade 3) in patients randomized to ClōSYS Oral Rinse versus placebo. Analysis will be performed by estimating the proportion with exact 95% binomial confidence interval for each group separately. Statistical testing will use a chi-square test. As an alternative, Fisher's Exact Test will be used if the minimum expected value is  $< 5$ .

The secondary statistical endpoint of time to onset of severe OM will be tabulated and the median week to onset will be computed for each group. Comparison will be performed using a Wilcoxon Rank Sum Test (as the values are unlikely to be normally distributed). Duration of severe OM (number of weeks) will be analyzed similarly. The proportion of patients in each group with RT interruption will be tabulated and compared using a chi-square test.

The longitudinal measurements of the OMWQ and PRO-CTCAE, microbiome components and pro-inflammatory cytokines will be compared between groups using a linear mixed-effects model to account for the correlation among the measurements within an individual.

To justify the proposed sample size, we assume that 9/10 (90%) of the placebo control patients will experience severe OM within the 6-week period. Ten patients per group will allow us to detect a decrease to 40% (4/10) in the patients randomized to ClōSYS® Unflavored Oral Rinse with 81% statistical power (assuming a one-sided alpha of 0.05).

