## SCHEMA

### **3. OBJECTIVES**

#### **3.1 Primary Objective**

- To evaluate and compare ClōSYS® Unflavored Oral Rinse effect on the incidence of severe OM as measured by the World Health Organization (WHO) scale ( $\geq$ WHO Grade 3)

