## **7. STUDY PLAN**

### **7.1 IP/treatment/intervention/device regimen**

Subjects will be stratified by whether or not they will be receiving concurrent systemic therapy and then randomly assigned to receive either ClōSYS® Unflavored Oral Rinse twice daily or placebo oral rinse twice daily from the start of RT to their 1-month RT follow-up appointment. Assignment of IP will be done in a double-blinded fashion. Both active rinse and placebo rinse will be formulated to look identical in appearance.

Subjects will receive verbal and written oral hygiene instructions and 11 bottles of either (16 oz. each) of ClōSYS® Unflavored Oral Rinse or placebo oral rinse. Subjects will also receive measuring cups for dispensing the rinse (15 ml per dose) and a diary for recording usage in order to track their rinsing adherence, as well as notating any subjective effects possibly attributable to the rinse.

Treatment with IP will start on the morning of day 1 of RT and subjects will be advised to use the IP (preferably after meals) at approximately 8 a.m.  $\pm$  3 hours and 8 p.m.  $\pm$  3 hours, with 15 mL per rinse for 30 seconds during each session. They will be instructed to take nothing by mouth for 20 minutes following their rinse to allow it to take effect. They will note in their patient's log the date, time, and duration of rinsing. Subjects will be instructed to continue with other standard oral hygiene practices we offer to our RT patients, including alkaline saline rinses, honey, miracle mouthwash, etc.

Baseline tobacco history including type of tobacco, number of pack-years, duration of smoking, and quit date if applicable will be recorded. This will be captured using the Tobacco Assessment Questionnaire (see section 27). Baseline dental evaluation counting number of teeth and generally graded condition (excellent, good, fair, poor) will be recorded. Baseline weight, BMI, and history of recent (3 months) weight loss will be recorded. Nutritional intake status (solids and liquids, liquids only, no oral intake) and utilization of enteral versus

parenteral feeding will be noted. HPV status of malignancy will be recorded. One week up until registration, concomitant medications will be collected.

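### For severe oral mucositis, Section 16 pre-specifies no between-arm effect estimate with an interval, and none of its analyses names the systemic-therapy stratum used to randomise

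*Combined protocol and SAP*

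**What the plan says.** The primary objective (Section 3.1) is to evaluate and compare the rinse's "effect on the incidence of severe OM as measured by the World Health Organization (WHO) scale", counting WHO grade 3 or higher. For that endpoint Section 16 says: "Analysis will be performed by estimating the proportion with exact 95% binomial confidence interval for each group separately". It continues: "Statistical testing will use a chi-square test", with Fisher's exact test if the smallest expected count is below 5. No risk difference, risk ratio or odds ratio is named, and no interval for a contrast between arms. Section 17.2 gives only the timing of the efficacy analysis.

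On allocation, Section 7.1 says: "Subjects will be stratified by whether or not they will be receiving concurrent systemic therapy and then randomly assigned". Section 9.2 adds envelopes and blocks, without a block size.

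The other Section 16 analyses are:
- time to onset of severe OM, and by extension duration: "Comparison will be performed using a Wilcoxon Rank Sum Test";
- the proportion "with RT interruption will be tabulated and compared using a chi-square test";
- questionnaires, microbiome components and cytokines: "compared between groups using a linear mixed-effects model".

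None of these names concurrent systemic therapy. The mixed-model sentence lists no covariates at all. Appendix B relates unspecified metadata variables to the microbiome, but it lies outside Section 16 and does not name systemic therapy.

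The sample-size paragraph assumes 90% versus 40% with 10 patients per arm and claims 81% power at one-sided alpha 0.05. Section 16 mentions a side only there; the sentences on the test give none.

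**The concern.** Section 4.2 hopes that the results will serve as preliminary data for a phase III trial. Planning such a trial needs the size of the between-arm difference and its uncertainty. The only uncertainty that the plan reports for severe OM is one interval per arm, and two marginal intervals do not convey the uncertainty of their difference. With about 20 evaluable patients, the choice of interval method also moves the limits by several points, so it should be made before unblinding.

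The stratum is the lesser gap. A factor thought important enough to control at allocation would normally appear somewhere in the analysis. Without it, the reader cannot see whether a chance imbalance in systemic therapy among evaluable patients accounts for part of the observed difference.

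**Working it through.** **Inputs.** From Section 16: placebo rate 0.90, active rate 0.40, 10 per arm, one-sided alpha 0.05, stated power 81%. From Section 7.1: one two-level stratum. The documents give no stratum sizes and no effect of the stratum on risk. Both are assumptions below, shown over a range.

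**1. The plan's own figure.** Arcsine approximation: h = 2·asin(√0.9) − 2·asin(√0.4) = 1.129. Power = Φ(1.129 × √5 − 1.645) = Φ(0.879) = 81.0%. Exact enumeration of the uncorrected one-sided chi-square gives 81.4%. The 81% therefore reproduces. At 9/10 versus 4/10 the smallest expected count is (1 + 6) × 10/20 = 3.5, so the plan's rule selects Fisher. At 10 per arm it does so unless exactly 10 of the 20 patients have severe OM (5.7% chance at 90% versus 40%). One-sided Fisher has 65.9% power.

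**2. What the plan would report at 9/10 versus 4/10.**
- Clopper-Pearson 95% intervals: 55.5-99.7% and 12.2-73.8%.
- Fisher p: 0.029 one-sided, 0.057 two-sided.

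**3. What is missing.** Wilson 95% limits are 0.5958 to 0.9821 (placebo) and 0.1682 to 0.6873 (active). Newcombe's interval for the difference of 0.50 is:
- lower: 0.50 − √[(0.90 − 0.5958)² + (0.6873 − 0.40)²] = 0.50 − 0.418 = 0.082;
- upper: 0.50 + √[(0.9821 − 0.90)² + (0.40 − 0.1682)²] = 0.50 + 0.246 = 0.746.

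So the result is 50 points, 95% interval 8 to 75. Other methods on the same data give 14 to 86 (Wald) and 7 to 77 (Agresti-Caffo). Coverage of the 95% Newcombe interval at 90% versus 40% is 96.7%.

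**4. Interval against test, all 121 tables at 10 per arm.** The 95% Newcombe interval lies above zero in 23 tables, exactly those where one-sided Fisher rejects at 0.05. Against two-sided Fisher at 0.05, it excludes zero without rejection in 6 tables. These carry 18.5% of trials at 90% versus 40% and include 9/10 versus 4/10 itself. Whether interval and test agree therefore depends on the side, which the test sentences do not state.

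**5. Stratified exact test.** The statistic is the number of placebo events. Its null distribution is the convolution of the two stratum hypergeometric distributions. Stratum rates are solved for a common odds ratio (OR) between strata within each arm, with arm averages of 90% and 40%. All power is one-sided at 0.05.

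| Assumed strata per arm (larger or equal stratum at higher risk) | OR | Stratified | Fisher |
|---|---|---|---|
| Equal, 5+5 to 8+2 | 1 | 66.0-66.3% | about 66% |
| Equal, 5+5 to 8+2 | 3 | 66.8-68.0% | about 66% |
| 8+2 vs 6+4, mean of both directions | 1 | 62.2% | 65.9% |
| same | 3 | 61.4% | 65.8% |
| same | 10 | 63.4% | 65.5% |

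With equal strata the gain is about 0 to 2 points. If the smaller stratum (3 or 2 per arm) is the one at higher risk, the stratified test has 66.1-66.2% at OR 3, which is practically no gain.

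**6. Effect of imbalance.** Take 8+2 versus 6+4, OR 3, larger stratum at higher risk. The expected unadjusted difference is 53.5 or 46.5 points, depending on which arm has the 8+2 split. Mantel-Haenszel weights are 8×6/14 = 3.43 and 2×4/6 = 1.33, and the weighted difference is 49.7 in both directions. Fisher power is 73.2% or 58.4% by direction; stratified power is 62.0% or 60.8%. This split is extreme: it has a 7.7% chance if arms of 8+4 each lose two patients at random.

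**7. Type I error.** Under the null at 8+2 versus 6+4, OR 1 to 10 and average rates 40-90%, one-sided Fisher rejects in at most 3.6% of trials and the stratified test in at most 2.0%.

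**The case against.** The strongest reply is that nothing is lost. The two proportions and their denominators determine the difference and its Newcombe interval, so anyone can compute them later, and the protocol calls this a pilot. The first part is true. What is lost is pre-specification: step 3 shows lower limits from 7 to 14 points on identical data.

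The stratum half can fairly be called a modest matter. The unstratified test is valid, and stratifying gains little or can lose power. That stands, and it is why the stratified test belongs in a sensitivity analysis. Silence is also not exclusion: the mixed-model sentence names no covariates, so the stratum is unspecified there.

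A reader might infer more than the documents support:
- **That the test is invalid because it ignores the stratum.** Step 7 shows no inflation of type I error.
- **That the plan judges the arms by overlap of their intervals.** It does not; it uses a test. At 90% versus 40% the per-arm intervals do overlap in 77% of the trials in which one-sided Fisher rejects. That describes how the display would look, not a decision rule.
- **That imbalance between arms must be small, or must be large.** Section 8.4 continues assessments after the rinse stops. But Section 8.3 takes some patients off study, Sections 9.6 and 15 end data collection at withdrawal, and Section 1.4 counts non-compliance against evaluability. The extent is open.

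**Conclusion.** The point holds as a gap in estimation and in matching the analysis to the design. At the design's own result the plan would give two wide, overlapping intervals and a p-value, where the quantity of interest is 50 points with a 95% interval of 8 to 75. That figure needs only the plan's assumed counts and the choice of Newcombe's method. The agreement of this interval with the test in all 121 tables rests on reading the primary test as one-sided at 0.05 with exactly 10 per arm.

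The stratum is secondary. All its power figures rest on assumed stratum sizes and odds ratios: a gain of about 0 to 2 points at OR 1-3 with equal strata, and a possible loss of about 2 to 4 points at an extreme split. They support using the stratum to check the result, not replacing the primary test. The change is worth making before unblinding because it is nearly free. The validity of the primary test does not depend on it.

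**What to change.** In Section 16:

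(a) Report the between-arm risk difference in severe OM with one pre-specified two-sided 95% Newcombe interval, labelled descriptive. State whether the primary test is one- or two-sided. If it is two-sided, say in advance that the test decides, since the interval can then exclude zero without rejection.

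(b) Keep the unstratified chi-square/Fisher rule as primary. Add, as a sensitivity analysis, the Mantel-Haenszel-weighted risk difference and an exact Cochran-Mantel-Haenszel test by concurrent systemic therapy.

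(c) Include the stratum as a fixed effect in the linear mixed models.

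Two further additions are not worth making. A 90% interval would exclude zero without one-sided Fisher rejecting in 7 tables (15.5% of trials at 90% versus 40%). A stratified Wilcoxon (van Elteren) test for onset and duration would split very few events, about 4 on active at the design rate. Section 16 also does not say how patients without severe OM enter those analyses.

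The cost is a few lines of SAP text and code and one degree of freedom per mixed model. The stratum is known at randomisation, so no new data are needed, and the power of the primary test is unchanged.
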